6.6.2. Laboratory parameters

Laboratory data (hematology and chemistry parameters) and change from baseline at each assessment time point will be summarized overall and by actual treatment group by means of descriptive statistics for continuous data.

Laboratory test results will be classified by the low/normal/high classification based on local laboratory normal ranges, if applicable. The number and percentage of patients will be summarized overall and by actual treatment group.

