## Menarini Group

Sponsor: A. Menarini Industrie Farmaceutiche Riunite S.r.l.

Amended Protocol Version 4.0 of 16.04.2018

Study Code: MEIF/16/MOF-Col/001

	
Monacolins act as reversible inhibitors of the 3-hydroxy-3-methyl-glutaryl-coenzyme A (HMG-CoA) reductase, a key enzyme in cholesterol biosynthesis. Besides the inhibition of HMG-CoA reductase, red yeast rice has been found to contain sterols, isoflavones and isoflavone glycosides, and monounsaturated fatty acids, all capable of lowering LDL cholesterol.

Aim of the Study	
The purpose of this study is to evaluate the effect of a combination of phytosterols and DIF1STAT® (fermented red rice titrated in 5 mg monacolin K), on modulation of lipid profile and other biomarkers in subjects with sub-optimal blood cholesterol levels.

Primary Objective	
To evaluate the effect of a nutraceutical combination over an 8-weeks period, on blood LDL-cholesterol levels in subjects with sub-optimal blood cholesterol levels.

Secondary Objectives	
To evaluate the effect of a nutraceutical combination on the following parameters following 8-weeks treatment, in subjects with sub-optimal blood cholesterol levels:
 

• Total blood cholesterol levels

• Blood HDL-cholesterol levels

• Blood non-HDL cholesterol levels

• Blood triglyceride levels

• Apolipoprotein B levels

• TC/HDL and LDL-C/HDL risk ratios

• Endothelial reactivity (Endocheck®)

• Glycemia, ALT, AST gamma-GT, creatinine, uric acid, CPK

Number and characteristics of Patients	
Ninety (90) subjects with sub-optimal blood LDL-cholesterol levels.

Number of Centers & Countries	
One Italian center

Study Duration (specify different study phases)	
Enrollment period: 6 months Screening period: 2 weeks Treatment period: 8 weeks The study will last 10 weeks per patient.

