### Laboratory parameters

Summary statistics of raw data and change from baseline at each assessment time point for each laboratory parameter will be presented overall and by treatment group.

Laboratory test results will be classified by the low/normal/high classification based on local laboratory normal ranges. A frequency table for low/normal/high classification will be presented overall and by treatment group for each laboratory parameter. A listing of all out of range laboratory parameters will be provided with values flagged to show the classification relative to the laboratory normal ranges.

Vital signs, weight, waist circumference, Index of Central Obesity (ICO), Body Mass Index (BMI), Hepatic Steatosis Index (HSI), Lipid Accumulation Product (LAP).

Heart rate and blood pressure will be measured in orthostatic and clinostatic position. Summary statistics of raw data and change from baseline at each assessment time point for each parameter will be presented overall and by treatment group.

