3.3. STUDY POPULATION

The study population consists of subjects, aged 30-75 years, with sub-optimal blood LDL-cholesterol levels (LDL-cholesterol = 115 -190 mg/dL and Triglycerides < 400 mg/dL). A total of at least 88 patients meeting the following inclusion and exclusion criteria are to be recruited.

Inclusion criteria

- Age 30-75 years
- LDL-cholesterol = 115-190 mg/dL

Statistical Analysis Plan

Sponsor: A. Menarini Industrie Farmaceutiche Riunite S.r.l.

Protocol number: MEIF/16/MOF-Col/001

- Triglycerides < 400 mg/dL
- Any cardiovascular therapy should be stable for type and dose for at least three months
- Signed, written informed consent

Exclusion criteria

- Intolerance to any ingredient of dietary supplement
- Patients already suffering from cardiovascular diseases or at high risk of developing cardiovascular diseases
- Myopathies
- Uncontrolled diabetes mellitus based on PI judgment
- Chronic renal failure (defined as eGFR<60ml/min/1.73m²) or liver failure (defined as AST and /or ALT>3 Upper Limit of Normal) (ULN)
- Body Mass Index > 32 kg/m²
- Therapy with statins or other drugs or supplements with effects on lipid metabolism
- Patients with acquired immunodeficiency
- Treatment with immunosuppressants
- Pregnant or breastfeeding women
- Women of childbearing potential not willing to use effective birth control methods
- Patients participating in or having participated in another clinical trial within the previous 3 months
- Current or recent history of drug or alcohol addiction based on PI judgment

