6. DEFINITION AND GENERAL METHODOLOGY

6.1. GENERAL METHODOLOGY

Statistical tables, figures, listings and analyses will be produced using SAS® for Windows release 9.4 (64-bit) or later (SAS Institute Inc., Cary, NC, USA). Continuous data will be summarized by mean, standard deviation (SD), median, 1st and 3rd quartile, minimum and maximum. Categorical data will be presented by absolute and relative frequencies (n and %) or contingency tables. Percentages will be computed considering subjects with non-missing information, if not differently specified.

DEFINITION OF BASELINE

The baseline period for the present study is defined as the visit 2 (Day 0 – baseline).

CODING OF THERAPIES AND MEDICAL TERMS

Baseline medical history, pre-existing conditions and adverse events will be coded using the Medical Dictionary for Regulatory Activities (MedDRA dictionary, English version 20.0). Prior and concomitant medications will be coded using the WHO Drug Dictionary version B2 Q4 2016.

MISSING OR PARTIAL DATES

For the computation involving dates, the following assumption will be made in case of partially missing information:

- Day missing => day will be replaced with 15
- Day and month missing => day will be replaced with 1, month will be replaced with 7
- Day, month and year missing => no imputation will be done

HANDLING OF MISSING DATA/IMPUTATION RULES/CENSORING RULES

No missing data imputation will be adopted.

HANDLING OF DROP-OUT PATIENTS

Not applicable.

MULTIPLICITY ISSUES

No alpha level adjustment for multiplicity will be adopted.

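### The only categorical laboratory safety table is low/normal/high, so no planned table counts, by arm, the patients with marked or new ALT, AST or CPK elevations

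*SAP*

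**What the plan says.** SAP 6.6.2 plans two laboratory outputs on the Tolerability set.

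- **Continuous.** "Laboratory data (hematology and chemistry parameters) and change from baseline at each assessment time point will be summarized overall and by actual treatment group". SAP 6.1 defines the statistics: "Continuous data will be summarized by mean, standard deviation (SD), median, 1st and 3rd quartile, minimum and maximum".
- **Categorical.** "Laboratory test results will be classified by the low/normal/high classification based on local laboratory normal ranges, if applicable", followed by "The number and percentage of patients will be summarized overall and by actual treatment group". No visit, worst value or comparison with the baseline class is named.

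Protocol 11.5 (Laboratory parameters) has the same categorical output: "A frequency table for low/normal/high classification will be presented overall and by treatment group for each laboratory parameter". It adds a listing that SAP 6.6.2 does not mention: "A listing of all out of range laboratory parameters will be provided with values flagged".

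The only multiple of the ULN in either document is an entry criterion, "liver failure (defined as AST and /or ALT>3 Upper Limit of Normal" (SAP 3.3; also Protocol 7.2). No multiple is given for CPK.

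**The concern.** The documents themselves make these tests relevant. The protocol's background says of the active ingredient that "Monacolins act as reversible inhibitors of the 3-hydroxy-3-methyl-glutaryl-coenzyme A (HMG-CoA) reductase". Myopathies and high transaminases are excluded at entry, and ALT, AST, gamma-GT and CPK are measured at all four visits.

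A single class above the normal range has two weaknesses. It merges elevations of very different size. It also merges elevations present before treatment with those that arise on treatment. The second weakness is a practical one here: entry excludes only transaminases above 3 x ULN and sets no CPK limit, so patients can be randomised with values already above normal.

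At stake is whether the report can state directly how many patients in each arm had a marked or new elevation.

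**Working it through.** **The documents' own figures.** Neither document states a figure for laboratory safety. The arm size used below comes from SAP 3.6: 35 evaluable per arm, and 35 / (1 - 0.20) = 43.75, rounded up to 44. This agrees with the plan and serves only as a denominator.

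**What each planned output can show about the number of patients with a marked or new elevation**

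- *Low/normal/high table:* counts patients, but has one class above normal and no link to the Visit 2 class. Each patient has post-baseline results at Visits 3 and 4, and the text does not say which one decides the class. Even if it is tabulated visit by visit, equal totals at Visit 2 and later can hide different patients moving in and out of the class.
- *Continuous summary:* the maximum shows the largest value at a visit, not how many patients had a large one.
- *ANCOVA on ALT, AST and CPK as secondary variables (SAP 6.5.3):* uses the change at Week 8 only, so a rise at Visit 3 that has resolved does not enter. It uses the FAS, which requires a Visit 4 LDL value. At the planned dropout, up to 44 - 35 = 9 patients per arm could be outside it. The rank fallback discards the size of an extreme value.
- *Adverse event tables:* an abnormal result enters only if the investigator considers it an adverse event (Protocol 10.2). No numerical criterion is given.
- *Protocol listing:* shows individual out-of-range values, but is not a count by arm.

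**Illustration on assumed data, in multiples of ULN.** Each arm has 44 patients, 34 of them at 0.6. Arm A has 10 at 1.1. Arm B has 5 at 1.1, 4 at 5 and 1 at 10.

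- High class: 10/44 = 22.7% in both arms.
- Mean, arm A: (34 x 0.6 + 10 x 1.1) / 44 = 31.4 / 44 = 0.71.
- Mean, arm B: (34 x 0.6 + 5 x 1.1 + 4 x 5 + 10) / 44 = 55.9 / 44 = 1.27.
- SD: 0.21 versus 1.85. Median and both quartiles: 0.6 in both arms.
- Maximum: 1.1 versus 10.
- Count above 3 x ULN: 0 versus 4 + 1 = 5.

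If arm B instead has 9 at 1.1 and 1 at 10, the high class is again 10/44 in both arms. The mean in arm B is (20.4 + 9.9 + 10) / 44 = 0.92, the maximum is again 10, and the count above 3 x ULN is 0 versus 1.

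The two versions of arm B have the same high count and the same maximum, yet five patients are above 3 x ULN in one and a single patient in the other. The means differ (1.27 versus 0.92), but a mean cannot be turned back into a count.

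**The case against.** A reader might infer that laboratory safety as a whole is reduced to three classes, so that a large rise would go unseen. The documents do not support that. The sentence just before the classification rule plans raw values and changes by arm and time point, and the planned statistics include the maximum. In the illustration, a single patient at 10 x ULN appears at once as that arm's maximum. With one centre and local reference ranges, comparing a maximum with the ULN is simple.

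Nor is the out-of-range listing lost. Protocol 11.5 requires it, SAP 1.1 declares no change from the protocol, and Protocol 11.8 requires deviations to be documented in the SAP, so the SAP's silence does not withdraw it. With about 44 patients per arm, someone could count marked elevations from the listing by hand. It would also be wrong to say that the trial could not answer the question: the data are reported, only the count is not tabulated.

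Finally, no objective in either document calls for tables by multiples of ULN, the 3 x ULN limit is an entry criterion and not an on-treatment endpoint, and this is an exploratory 8-week study.

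All of this stands, and it limits the point to presentation. It does not remove it. A maximum is one value, a hand count from a listing is not a prespecified result by arm, and the ANCOVA and adverse event routes have the gaps shown above.

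**Conclusion.** The narrow point holds. The sole categorical laboratory summary merges slight with marked elevations and pre-existing with new ones, and no other planned table supplies the missing count by arm.

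Its size is small. It concerns how safety data are reported, contradicts no other passage, and has no bearing on the LDL analysis. The improvement is worth making but not essential.

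That the count is missing rests on the text alone. The figures 10/44, 1.1 versus 10, and 0 versus 5 rest on invented values chosen to show what each output can distinguish. The documents give no expected rate of elevations, so nothing here predicts how many patients would be affected.

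**What to change.** In SAP 6.6.2, on the Tolerability set and by treatment actually received:

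- **ALT and AST:** add a shift table from the Visit 2 class to the worst post-baseline class, with classes up to ULN, above 1 to 3 x ULN, and above 3 x ULN. The 3 x ULN cut is borrowed from the entry criterion only as a reporting category and implies no clinical rule.
- **CPK:** add the same shift table, with categories in multiples of ULN that the sponsor fixes before database lock, since the documents give none.
- **Worst value:** state which results count, for example Visit 3, Visit 4 and any assessment after early discontinuation.
- **Listing:** restate the Protocol 11.5 listing of out-of-range results, so that the SAP's output list is complete.

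The cost is one extra table from data already collected and one sentence for the listing. No test, visit or clinical rule changes.

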6.6.3. Vital signs/Physical examination

Vital signs, heart rate and blood pressure, calculated as average of three measurements both in orthostatic position and clinostatic position, will be summarized at each assessment time point overall and by actual treatment group by means of the usual descriptive statistics for continuous variables. Change from baseline on average of measurements at each assessments time point will be also summarized. The three measurements collected in orthostatic position and clinostatic position will be only listed.

Anthropometric data and change from baseline at each assessments time point will be summarized at each assessment time point overall and by actual treatment group by means of the usual descriptive statistics for continuous variables.

6.6.4. Other safety parameters

Pregnancy test results at visit 4 will be listed.

6.7. SUBGROUP ANALYSES

No subgroup analyses are currently planned.

6.8. INTERIM ANALYSIS/DMC

No interim analysis is planned.

Statistical Analysis Plan

Sponsor: A. Menarini Industrie Farmaceutiche Riunite S.r.l.

Protocol number: MEIF/16/MOF-Col/001

7. REFERENCES

Not applicable.

8. APPENDIX

Not applicable.
